Run-in Failure	A subject who is screened but not randomized/treated after the run-in period (where run-in period requires adjustment to subject's intervention or other treatment)	
Screen Failure	A subject who did not meet one or more criteria that were required for participation in the study	
Source Data/Document	Source data refers to the initial record, document, or primary location from where data comes. The data source can be a database, a dataset, a spreadsheet or even hard-coded data, such as paper or eSource	
Start of the clinical trial	The start of the clinical trial is defined as the signature of the informed consent by the first subject	
Study treatment	Any single drug or combination of drugs or intervention administered to the subject as part of the required study procedures	
Study treatment discontinuation	When the subject permanently stops taking any of the study drug(s) prior to the defined study treatment completion date (if any) for any reason; may or may not also be the point/time of study discontinuation	
Subject	A trial participant (can be a healthy volunteer or a patient)	
Subject number	A unique number assigned to each subject upon signing the informed consent. This number is the definitive, unique identifier for the subject and should be used to identify the subject throughout the study for all data collected, sample labels, etc.	

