## Run-in Epoch

[figure not shown]
A 6-week run-in epoch will commence on **Day -42**. First, eligible patients will discontinue methotrexate and azathioprine. Hydroxychloroguine will be allowed to continue as background therapy. Then, on **Day -28** (2 weeks after discontinuation of methotrexate or azathioprine), patients will undergo a full safety assessment, a "Clinical Status Evaluation (CSE)", and enter into a steroid (prednisone or equivalent; see Table 17-1-Appendix 3) titration algorithm. CSE will consist of a 6-minute walk test, spirometry assessments, and an assessment of dyspnea (Modified Medical Research Council [mMRC] breathlessness scale). The CSE serves as an additional safety evaluation and will serve to establish the patient's current clinical status (Clinical Status Determination [CSD]) as compared to their status at Day -42 (Figure 3-2). The CSE will be performed at each subsequent visit, prior to the titration of steroids, and the CSD will guide selection of the next dose of steroids (Figure 3-3). Steroid titration will continue through the run-in epoch: and steroid titration will also continue through the treatment epoch. Patients with CSD of "improved" or "stable" will decrease steroid dose by 1-step on the dosing scale (Figure 3-4). (Note: To prevent Addisonian crisis, steroids will not be tapered below a physiologic dose (2.5 mg/day); and steroid tapering will follow a very slow regimen, as per protocol – i.e., modest decreases in dose, no more frequent than every four weeks). Patients with CSD of "deteriorating" will be ineligible to continue the study (if "deteriorating" is determined during the run-in epoch); or they will increase their steroid dose by 1-step (if "deteriorating" is determined during the treatment epoch). [ $^{18}$ F]-FDG PET/CT will be performed prior to the first dose (**Day -2 (± 1**)) and again at the end of the treatment epoch (**Day 113**).

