# 3.2 Rationale for study design

The rationale for key elements of this study are as follows:

- Placebo controls: The placebo group is used to define the natural history of disease under the study's conditions. Comparison of placebo to the active group provides the most rigorous test of efficacy. Since no drugs are currently approved for the treatment of sarcoidosis, inclusion of a placebo arm is considered to be ethical; and the risk-benefit of placebo treatment is considered to be favorable. (Note: the potential benefits of alternative treatments, such as TNF inhibitors, are unproven/unknown, risk-benefit of alternative treatments are unfavorable, and such treatments are prohibited by this protocol).
- **Randomization:** Randomization is used to avoid "selection bias" in the assignment of subjects to treatment groups. Randomization also serves to balance the treatment groups with respect to many known and unknown confounding variables; and randomization forms the basis of assumptions for our statistical tests.
- **Blinding:** Conscious and unconscious biases are avoided ("detection bias" and "reporting bias", pertaining to outcome assessment) by ensuring that patients and investigators are unaware of treatment assignment.
- **Run-in epoch:** During this epoch, adjustments are made to background therapy in an effort to harmonize all the patients before commencement of the treatment epoch.
- **Discontinuation of methotrexate and azathioprine during the run-in epoch:** In clinical practice, immunosuppressants are often interrupted while the patient is closely observed for evidence of clinical change. This protocol mimics the immunosuppressant interruption that is frequently employed in clinical practice. This design allows a more robust evaluation of the efficacy of CMK389 while minimizing the potentially masking effects of immunosuppressant therapy.
- Steroid titration algorithm: Judicious titration of corticosteroids is common practice for a patient with sarcoidosis who is doing well; conversely, the dose of steroids is typically increased for a patient with sarcoidosis who is doing poorly. Within the context of this clinical trial, adjustment of steroids will be allowed. However, to avoid the introduction of "performance bias" by individual sites and investigators, all steroid titrations will be performed according to the rules of a pre-determined algorithm.

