### Highly effective contraception methods include:

- Total abstinence (when this is in line with the preferred and usual lifestyle of the subject. Periodic abstinence (e.g. calendar, ovulation, symptothermal, post-ovulation methods) and withdrawal are not acceptable methods of contraception
- Male/female sterilization
- Use of oral, injected or implanted hormonal methods of contraception or placement of an intrauterine device (IUD) or intrauterine system (IUS) or other forms of hormonal contraception that have comparable efficacy (failure rate <1%), for example hormone vaginal ring or transdermal hormone contraception

In case of use of oral contraception, women should be stable on the same pill for a minimum of 3 months before taking investigational drug.

- 22. Other history or current diagnosis of ECG abnormalities not due to cardiac sarcoidosis at screening as determined by the investigator and based on the totality of the safety information to indicate significant safety risk. The following should be considered by the investigator in guiding the determination as part of the overall assessment, but should not be considered in isolation:
  - PR > 200 msec
  - QRS complex > 120 msec
  - QTcF > 450 msec (males)
  - QTcF > 460 msec (females)
- 23. Concomitant clinically significant cardiac arrhythmias, e.g. sustained ventricular tachycardia, and clinically significant second or third degree AV block without a pacemaker
- 24. Significant illness which has not resolved within two weeks prior to initial dosing
- 25. Donation or loss of 400 mL or more of blood within eight weeks prior to initial dosing, or longer if required by local regulation
- 26. Any surgical or medical condition which might significantly alter the absorption, distribution, metabolism, or excretion of drugs, or which may jeopardize the subject in case of participation in the study. The investigator should make this determination in consultation with the sponsor and in consideration of the subject's medical history and/or clinical or laboratory evidence.
- 27. Clinical Status Determination (CSD) of "deteriorating" at Day-28 (V102) or Day 1 (V201)

- 28. A diagnosis of Lofgren's syndrome
- 29. History of pancreatitis
- 30. Other pulmonary disease (i.e., asthma, bronchiectasis, COPD, etc.) unrelated to sarcoid as determined by the investigator
- 31. Active drug or alcohol abuse (as defined by the investigator) within 3 months prior to screening.

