### Page 58 Protocol No. CCMK389X2201

Confidential

Novartis	Confidential
Amended Protocol Version v08 (Clean)	

Page 59
Protocol No. CCMK389X2201

Epoch	Pregnancy Testing Period (WOCBP Only) 				
Visit Name	Pregnancy Testing (WOCBP Only)	End of Study #2			
Visit Numbers 	401	499			
Days	225 ±3	253 ±3			
Pregnancy and assessments of fertility	S 	S 			
Serious Adverse Event - Only Pregnancies Reported 	Х	X			
Study/Epoch completion information		X			

x Assessment to be recorded in the clinical database or received electronically from a vendor

S- source documentation at the study site

 Visit structure given for internal programming purpose only

 Unless specified otherwise, assessments at 0 min should be done pre-dose

 Can be done at Day -1 instead of Day 1 if needed.

 Determined by QuantiFERON TB-Gold test

 Serum pregnancy test

 Urine pregnancy test

 Chemistry panel must be done under fasting conditions at all visits

 Only for patients who don't have an historical chest x-ray within 12 months from screening

 HRCT at screening should be performed after all other screening assessments for eligibility. A historical HRCT obtained within 12 months prior to screening may be used instead and sent to the central reader for analysis.

 Fasting glucose and [F]FDG-PET/CT must be done on a different day than the other assessments of V299 or after all other V299 assessments are completed on the same day.

 The [F]FDG-PET/CT requires a blood glucose level below 11 mmol/L. The measurement is performed by finger prick at site before [F]FDG-PET/CT is performed

 Clinical Status Determination includes the following: 6-minute walk distance, FVC, FEV1 and mMRC dyspnea score. Complete the form (found in the SOM) and use as a guide for CSE

 Discontinue methotrexate and azathioprine

 Patients with CSD of "deteriorating" will be ineligible to continue the study (during the run-in epoch); or they will increase steroid dose by 1-step (during the treatment epoch). See study design Section 3.1

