#### 8.4.2 **Discontinue Sarcoidosis Immunosuppressant Therapy**

During the run-in epoch eligible patients will discontinue methotrexate and azathioprine. The patient's immunosuppressant therapy may be restarted after V299 is completed, at the Investigator's discretion.

Page 63

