### 9.2.2 SAE reporting

#### Screen Failures & Run-In Failures

Note the following requirement for Screen Failures: SAEs occurring after the subject has provided informed consent until the time the subject is deemed a Screen Failure must be reported to Novartis.

For subjects considered Run-In Failures, SAEs occurring after the subject has provided informed consent until the time the subject is deemed a Run-In Failure must be reported to Novartis.

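### Mandatory SAE reporting for run-in failures stops at the failure decision, after the protocol has withdrawn methotrexate or azathioprine; a 30-day tail would be a cheap improvement

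*Protocol*

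**What the plan says.** Patients enter on prednisone plus methotrexate or azathioprine, each taken for at least 6 months (Protocol 4.1). At V101 (Day -42) the immunosuppressant is stopped. Section 8.4.2 states: "During the run-in epoch eligible patients will discontinue methotrexate and azathioprine". Section 3.2 defends this by reference to clinical practice, in which "immunosuppressants are often interrupted while the patient is closely observed for evidence of clinical change".

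Clinical status is determined at V102 (Day -28) and again at V201 (Day 1). A stable or improved patient steps the steroid dose down. During the run-in, "Patients with CSD of 'deteriorating' will be ineligible to continue the study" (Section 3.1), and exclusion criterion 27 applies the same rule at V102 and V201. The glossary describes a run-in failure as "A subject who is screened but not randomized/treated after the run-in period".

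For these patients Section 9.2.2 makes SAEs reportable from consent "until the time the subject is deemed a Run-In Failure must be reported to Novartis". The sentence for screen failures has the same form. The 30-day extension beyond the End of Study visit appears only under the Treated Subjects heading of that section.

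**The concern.** Screen failures and run-in failures share a cut-off but are not in the same position. A screen failure leaves with background therapy untouched. A run-in failure leaves after the protocol has removed a long-standing immunosuppressant and, if failing at V201, possibly after one steroid step-down as well. Some fail because they are already worsening.

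A serious flare shortly after the failure decision is a foreseeable result of a change the protocol required. With reporting closed at that decision, the sponsor may not learn of it while other patients are still entering the same run-in. What is at stake is knowledge of harm from the run-in, not any efficacy result.

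**Working it through.** The plan gives no figure to reproduce. The check is a subtraction of visit days and a comparison of the provisions that might cover a late SAE.

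**Inputs.** Table 8-1 gives V101 at Day -42 ±1, V102 at Day -28 ±1 and V201 at Day 1. Footnote 3 says of the V201 assessments, including the clinical status form: "Can be done at Day -1 instead of Day 1 if needed". There is no Day 0, which agrees with a 6-week run-in from Day -42 to Day 1. Failure is assumed to be decided on the day of the status determination.

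**Days from the immunosuppressant stop to the end of mandatory reporting**

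| Failure at | Nominal | Shortest | Longest |
|---|---|---|---|
| V102 | 42 - 28 = 14 | Day -41 to Day -29 = 12 | Day -43 to Day -27 = 16 |
| V201 | Day -42 to Day 1 = 42 | Day -41 to Day -1 = 40 | Day -43 to Day 1 = 43 |

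**With a 30-day tail**

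- V102: 14 + 30 = 44 days (42 to 46).
- V201: 42 + 30 = 72 days (70 to 73).

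**Provisions that might already cover a new SAE after the decision**

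- *9.1, follow-up of detected AEs.* An AE must be followed until it clears or is considered permanent. This covers worsening of an event found before failure. It does not cover an event that starts afterwards.
- *9.1, late events.* SAEs believed related to study treatment must be reported even after the observation period. The glossary defines study treatment as "Any single drug or combination of drugs or intervention administered to the subject as part of the required study procedures". Protocol-directed steroid titration might fit that wording. Stopping a background drug fits it less well, and 6.1.3 limits treatment in the trial to investigational drug and placebo.
- *9.1, AE definition.* The AE period closes at the end of study visit, and individual SAE reporting is referred to 9.2.2.
- *9.2.2, Treated Subjects.* The 30-day tail and the open-ended duty to report progression or recurrence both stand under this heading.
- *8.1, early discontinuation.* This gives at most one exit visit with AE recording. It does not name run-in failures and sets no SAE window.
- *9.8, early phase monitoring.* Investigators must tell the sponsor of clinically relevant observations, and the sponsor must pass new safety information to sites. No window or deadline after failure is given.
- *7.5, 10.4 and 11.1.* The pausing rules count events related to the drug, no data monitoring committee is required, and the safety set needs at least one dose. None of these would pick up such an SAE.

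**Cost of one call per run-in failure.** No failure rate is stated. If a fraction f of those entering the run-in fail for any cause and 66 are randomised, the number of failures is 66/(1 - f) - 66:

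- f = 0.10: 73.3 - 66 = 7.3, about 7 calls.
- f = 0.20: 82.5 - 66 = 16.5, about 17 calls.
- f = 0.30: 94.3 - 66 = 28.3, about 28 calls.

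These are calls, not missed SAEs.

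**The case against.** Four points on the other side carry weight.

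1. A reader might infer that run-in failures have no reporting rule. They do. Section 9.2.2 gives them their own sentence with a definite end, and the point concerns where that end falls.
2. A reader might infer that patients who fail through deterioration have their worsening go unrecorded. A deteriorating status needs two or more parameters worse (such as a 15% relative fall in FVC or a 50 m loss in walk distance), or an mMRC change of at least 2 points (Figure 3-2). Worsening on that scale is not automatically an AE. It would usually meet the 9.1 definition, though, and would then have to be followed up. The patients already getting worse are therefore the best covered.
3. Section 9.8 is a real route to the sponsor and is not limited to treated subjects. It is general and sets no time limit, so it narrows the gap without closing it.
4. The Site Operations Manual, which 9.1 cites for AE collection in subjects who fail screening, could not be consulted and might already deal with run-in failures.

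The passage in 3.2 on close observation describes patient care, not reporting to a sponsor. Nor do the documents support reading the cut-off as leaving patients untreated: nothing supplied prevents a run-in failure from resuming the immunosuppressant or raising the steroid dose. The proposal improves reporting and adds little to care.

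**Conclusion.** The point holds in a narrow form. Mandatory reporting for run-in failures ends at the failure decision, about 14 days after the immunosuppressant stop at V102 and about 42 days after it at V201. No supplied text requires a new SAE starting after that to be reported within a set window. This rests on failure being decided on the day of the status determination, and on the Site Operations Manual not already filling the gap.

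The number of SAEs affected is unknown and could be zero. A reader might take the 30-day tail for treated subjects as a standard that run-in failures are denied. The two groups are not alike, and 30 days here is a pragmatic choice. Nor does the point bear on the trial's results: run-in failures are outside the safety set, and the primary analysis, sample size and randomised safety comparison stay as they are. It is a low-cost improvement in the sponsor's knowledge of run-in harm, not a flaw in the analysis.

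**What to change.** Amend Section 9.2.2 along these lines:

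> For run-in failures who stopped methotrexate or azathioprine at V101, any SAE with onset up to 30 days after the failure decision is reported within 24 hours of the site learning of it. The site makes one telephone contact at or just after day 30 and documents its attempts if the patient is not reached. If consent has been withdrawn, no contact is made except as Section 7.3 allows.

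Timing the call at the end of the window matters, because an early call would miss later events. Show these SAEs in a separate listing of non-randomised subjects, and align the Site Operations Manual if it differs.

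The cost is a written amendment with the approvals in Section 13.1, which can be bundled with another; one call per affected run-in failure (about 7, 17 or 28 under the assumed rates of 10%, 20% or 30%); and one small listing. No visit or procedure is added.

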#### **Treated Subjects**

To ensure subject safety, every SAE, regardless of causality, occurring after the subject has provided informed consent and until 30 days after the End of Study visit must be reported to Novartis within 24 hours of learning of its occurrence as described below.

All follow-up information for the SAE including information on complications, progression of the initial SAE and recurrent episodes must be reported as follow-up to the original episode immediately, without undue delay, and under no circumstances later than within 24 hours of the investigator receiving the follow-up information. An SAE occurring at a different time interval or otherwise considered completely unrelated to a previously reported one must be reported separately as a new event.

Follow- up information provided must describe whether the event has resolved or continues, if and how it was treated, whether the blind was broken or not (if applicable) and whether the subject continued or withdrew from study participation. Each re-occurrence, complication, or progression of the original event must be reported as a follow-up to that event regardless of when it occurs.

If the SAE is not previously documented in the Investigator's Brochure or Package Insert (new occurrence) and is thought to be related to the study treatment a Chief Medical Office and Patient Safety (CMO& PS) Department associate may urgently require further information from the investigator for Health Authority reporting. Novartis may need to issue an Investigator Notification (IN) to inform all investigators involved in any study with the same study treatment that this SAE has been reported. Suspected Unexpected Serious Adverse Reactions (SUSARs) will be collected and reported to the competent authorities and relevant ethics committees in accordance with EU Guidance 2011/C 172/01 or as per national regulatory requirements in participating countries.

Follow the detailed instructions outlined in the Site Operations Manual regarding the submission process for reporting SAEs to Novartis. Note: SAEs must be reported to Novartis within 24 hours of the investigator learning of its occurrence/receiving follow-up information.

# 9.3 Liver safety monitoring

To ensure subject safety and enhance reliability in determining the hepatotoxic potential of an investigational drug, a standardized process for identification, monitoring and evaluation of liver events has to be followed.

Please refer to Table 15-1 Appendix 1 for complete definitions of liver events.

#### Follow-up of liver events

Every liver event defined in Table 15-1 Appendix 1 should be followed up by the investigator or designated personnel at the trial site, as summarized below. Additional details on actions required in case of liver events are outlined in Table 15-1 Appendix 1.

• Repeating liver chemistry tests (ALT, AST, TBL, PT/INR, ALP and G-GT) to confirm elevation within 48-72 hours.

These liver chemistry repeats should always be performed using the central laboratory, with the results provided via the standard electronic transfer. If results will not be available from the central laboratory within 24 hours, then the repeats can also be performed at a local laboratory to monitor the safety of the subject. If a liver event is subsequently reported, any local liver chemistry tests previously conducted that are associated with this event should have results reported on the unscheduled local laboratory CRF.

Confidential

- If the initial elevation is confirmed, close observation of the subject will be initiated, including consideration of treatment interruption if deemed appropriate.
- Discontinuation of the investigational drug (refer to Section 7.2 (Discontinuation of study treatment), if appropriate
- Hospitalization of the subject if appropriate
- Causality assessment of the liver event
- Thorough follow-up of the liver event should include:
  - Repeating liver chemistry tests two or three times weekly. Testing should include ALT, AST, ALP, PT/INR, and GGT. If total bilirubin is elevated > 2 x ULN, fractionation into direct and indirect bilirubin is required. To rule out muscular origin of transaminase elevations, CPK should be measured along with liver chemistry tests. Frequency of retesting can decrease to once a week or less if abnormalities stabilize or the study drug has been discontinued and the subject is asymptomatic. Retesting should be continued up to resolution.
  - Obtaining a more detailed history of symptoms and prior or concurrent diseases.
  - Obtaining a history of concomitant drug use (including nonprescription medications and herbal and dietary supplement preparations), alcohol use, recreational drug use, and special diets.
  - Exclusion of underlying liver disease, as specified in Table 15-3 Appendix 1.
  - Imaging such as abdominal US, CT or MRI, as appropriate
  - Obtaining a history of exposure to environmental chemical agents.
  - Considering gastroenterology or hepatology consultations.

All follow-up information, and the procedures performed must be recorded as appropriate in the CRF. Refer to the Site Operations Manual for additional details.

